Appendix F: Adverse Events of Clinical Interest

Below please see the definition and searching criteria for adverse events of clinical interest.

Definition of Adverse Event of Special Interest and Events of Clinical Interest (MedDRA version 24.0)

1. Adverse Event of Special Interest (AESI)

The following preferred terms (PT) for the ventricular arrhythmias AESI include:

- Torsade de pointes
- Ventricular arrhythmia
- Ventricular extrasystoles
- Ventricular fibrillation
- Ventricular flutter
- Ventricular tachyarrhythmia
- Ventricular tachycardia

2. Events of Clinical Interest

The Events of Clinical Interest (ECIs) have been identified based on preclinical findings, emerging data from clinical studies relating to acalabrutinib, and pharmacological effects of approved Bruton's tyrosine kinase (BTK) inhibitors. The adverse events (AEs) selected for dedicated analysis were evaluated using Standardized MedDRA Queries (SMQs), where available, by System Organ Classes (SOCs), or by Sponsor-defined baskets of MedDRA Adverse Event Grouped Terms.

Category	Subcategory	Definition
Cardiac events		
• SOC Cardiac disorders
	Atrial fibrillation	
• PT Atrial fibrillation• PT Atrial flutter

Ventricular tachyarrhythmias	
• PT Torsade de pointes• PT Ventricular fibrillation• PT Ventricular flutter• PT Ventricular tachyarrhythmia• PT Ventricular tachycardia
Cytopenias – Anemia	
• SMQ Haematopoietic erythropenia [narrow + broad]
Cytopenias – Leukopenia	
• SMQ Haematopoietic leukopenia [narrow + broad]
Neutropenia	
• PT Band Neutrophil count decreased• PT Band neutrophil percentage decreased• PT Cyclic neutropenia• PT Febrile Neutropenia• PT Idiopathic neutropenia• PT Neutropenia• PT Neutropenic infection• PT Neutropenic sepsis• PT Neutrophil count decreased• PT Neutrophil percentage decreased
Other leukopenia	
• SMQ Haematopoietic leukopenia [narrow + broad] excluding PTs for neutropenia above
Cytopenias - Thrombocytopenia	
• SMQ Haematopoietic thrombocytopenia [narrow + broad]
Hemorrhage	
• SMQ Haemorrhage terms (excl laboratory terms)
Major hemorrhage	
• As per definition (see Section 3 below)

Hepatotoxicity	
SMQ [narrow] Hepatic failure, fibrosis and cirrhosis and other liver damage-related conditionsSMQ [narrow] Hepatitis, non-infectiousSMQ [narrow] Liver related investigations signs
Hypertension	
SMQ Hypertension [narrow]
Infections	
SOC Infections and infestations
Interstitial lung disease/Pneumonitis	
SMQ [narrow] Interstitial lung disease
Second primary malignancies	
SMQ Malignant tumours (including Haematological malignant tumours SMQ and Non-haematological malignant tumours SMQ)SMQ Malignant lymphomas [narrow]SMQ Myelodysplastic syndrome [narrow]
Second primary malignancies (excluding non melanoma skin)	
The above excluding PTs mapping to HLT Skin neoplasms malignant and unspecified (excluding melanoma)
Tumor lysis syndrome	
PT Tumour lysis syndrome

AE=adverse event; ALT=alanine aminotransferase; AST=aspartate aminotransferase; HLT=high-level term; ISS=integrated safety summary; PT=preferred term; SAE=serious adverse event; SMQ=Standardised MedDRA Query; ULN=upper limit of normal. MedDRA version 24.0

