- Subjects who meet the criteria for PR with the exception of having less than a 50% reduction in peripheral lymphocyte count AND absolute lymphocyte count $> 5,000/\mu\text{L}$ will be considered a PRL. These subjects should continue to be followed on therapy and response status updated if the lymphocyte count does decrease by $\geq 50\%$ or absolute lymphocyte count $< 5,000/\mu\text{L}$ is achieved.

Progressive Disease: Progressive disease will be characterized by any one of the following events:

- $\geq 50\%$ increase in the products of at least 2 lymph nodes on 2 consecutive determinations 2 weeks apart (at least 1 lymph node must be $\geq 2 \text{ cm}$); appearance of new palpable lymph nodes
- $\geq 50\%$ increase in the size of the liver and/or spleen as determined by measurement below the respective costal margin; appearance of palpable hepatomegaly or splenomegaly, which was not previously present
- Transformation to a more aggressive histology (i.e., Richter's syndrome or PLL with $\geq 56\%$ prolymphocytes)
- The progression of any cytopenia (unrelated to autoimmune cytopenia), as documented by a decrease of Hgb levels $> 2 \text{ g/dL}$ or to $< 10 \text{ g/dL}$, or by a decrease of platelet counts $> 50\%$ or to $< 100,000/\mu\text{L}$, which occurs at least 3 months after the initiation of treatment, defines disease progression, if the marrow biopsy demonstrates an infiltrate of clonal CLL cells. During therapy, cytopenias cannot be used to define disease progression.

Stable Disease: Subjects who do not fulfill the criteria for CR or PR as defined above but do not exhibit progressive disease will be considered as having stable disease (SD).

Table 14: IWCLL Response Assessment Criteria

Response	Lymphocytes	Bone Marrow	Physical Examination ^a (Nodes, Liver, Spleen)	Peripheral Blood
CR*	Lymphocytes $<4 \times 10^9/L$	Normocellular $<30\%$ lymphocytes No B-lymphoid nodules	Normal (e.g., no lymph nodes >1.5 cm)	ANC $>1.5 \times 10^9/L^b$ Platelets $>100 \times 10^9/L^b$ Hemoglobin >11.0 g/dL (untransfused) ^b
CRi	Lymphocytes $<4 \times 10^9/L$	Hypocellular $<30\%$ lymphocytes	Normal (e.g., no lymph nodes >1.5 cm)	Persistent anemia, thrombocytopenia, or neutropenia related to drug toxicity
nPR	CR with the presence of lymphoid nodules in the bone marrow, which reflect residual disease			

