10.5.1 Second Primary Malignancies

AEs for malignant tumors reported during a study should generally be assessed as SAEs. If no other seriousness criteria apply, the “Important Medical Event” criterion should be used. In certain situations, however, medical judgment on an individual event basis should be applied to clarify that the malignant tumor event should be assessed and reported as a nonserious AE. For example, if the tumor is included as medical history and progression occurs during the study but the progression does not change treatment and/or prognosis of the malignant tumor, the AE may not fulfill the attributes for being assessed as serious, although reporting of the progression of the malignant tumor as an AE is valid and should occur. Also, some types of malignant tumors, which do not spread remotely after a routine treatment that does not require hospitalization, may be assessed as nonserious; examples in adults include Stage 1 basal cell carcinoma and Stage 1A1 cervical cancer removed via cone biopsy.

The above instruction applies only when the malignant tumor event in question is a new malignant tumor (i.e., it is not the tumor for which entry into the study is a criterion and that is being treated by the investigational product under study and is not the development of new or progression of existing metastasis to the tumor under study). Malignant tumors that—as part of

normal, if rare, progression—undergo transformation (e.g., Richter's transformation of B cell CLL into diffuse large B cell lymphoma) should not be considered a new malignant tumor.

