13.1 Adverse Events

AEs will be coded using the Medical Dictionary for Regulatory Activities (MedDRA v 24.0) reporting system. The investigator will grade AEs according to the National Cancer Institute Common Terminology Criteria for Adverse Events (NCI-CTCAE) v4.03 for AEs.

Hematologic toxicity is assessed by the investigator according to IWCLL 2008 guidelines for Cohorts 1 and 2, and NCI CTCAE v4.03 for Cohorts 3 and 4. TEAEs are defined as those events that occur on or after the first dose of study drug, through the treatment phase, and within 30 days following the last dose of study drug.

All TEAEs will be summarized by cohort as treated. For each cohort, AE incidence rates will be summarized with frequency and percentage by system organ class and preferred term, and the denominator for the AE incidence rate will be based on the number of subjects treated in that cohort unless otherwise specified. In addition, AE incidence rates will also be summarized by severity, and relationship to study drug. Relationship to study drug, per the investigator's judgment, is recorded on the CRF.

Subjects with multiple occurrences of events for a given preferred term, system organ class, or overall will be counted only once at the maximum severity, and strongest relationship to study drug for each preferred term, system organ class, and overall, respectively.

Summaries will be presented for:

- treatment-emergent AEs
- treatment-emergent serious adverse events (TESAEs)
- treatment-related TEAEs
- treatment-related TESAEs
- AEs leading to study drug discontinuation or dose modifications or dose delay
- treatment-emergent fatal (Grade 5) AEs

13.2 Adverse Events of Clinical Interest.

Adverse events of clinical interest (ECIs) are specified in Appendix F. Subject incidence rates of AEs of clinical interest will be summarized similarly to TEAEs by cohort.

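### The SAP search for second primary malignancies has no exclusion for CLL/SLL/PLL or Richter's transformation, so any such event reported as a TEAE would be counted as a second cancer, contrary to Protocol 10.5.1

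*SAP*

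**What the plan says.** SAP Appendix F lists the events of clinical interest with their search criteria. The row for second primary malignancies combines three queries: "SMQ Malignant tumours (including Haematological malignant tumours SMQ and Non-haematological malignant tumours SMQ", "SMQ Malignant lymphomas [narrow", and the narrow myelodysplastic syndrome query. A second row repeats the category with one exclusion: "The above excluding PTs mapping to HLT Skin neoplasms malignant and unspecified (excluding melanoma". Neither row mentions CLL, SLL, PLL or transformation. SAP 13.2 then says: "Subject incidence rates of AEs of clinical interest will be summarized similarly to TEAEs by cohort". It describes no medical review of what the searches return.

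Protocol 10.5.1 gives the reporting guidance for second primary malignancies. It applies only to a new malignant tumor, meaning among other things that "it is not the tumor for which entry into the study is a criterion". It also says that "transformation (e.g., Richter's transformation of B cell CLL into diffuse large B cell lymphoma) should not be considered a new malignant tumor". Protocol Section 9 lists among the criteria for progressive disease: "Transformation to a more aggressive histology", naming Richter's syndrome and prolymphocytic change.

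Protocol 10.3 controls what reaches the adverse event data. Progression that clearly fits the underlying cancer is not an adverse event. If there is doubt whether an event is due only to the study disease, it must be reported as an AE or SAE.

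**The concern.** The trial population has a haematological malignancy. A search that deliberately includes haematological malignancies and lymphomas, with nothing to remove the study disease, can return the disease itself or its transformation. The output would label these as second cancers, while the protocol says they are not new tumors.

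Second primary malignancy is a named acalabrutinib risk (Protocol 6.4.1.4), and safety is a primary objective in all four cohorts (Protocol 1.1). Transformation is disease progression and therefore already an event in the PFS analysis (SAP 12.2.3). If it also appears under second primary malignancies, a treatment failure is presented as a drug toxicity. With cohorts of 26, 19, 12 and 12, one misplaced subject visibly changes the reported rate.

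**Working it through.** The plan states no figure for this category, so there is nothing to reproduce. The check compares the texts and then does a small sensitivity calculation.

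**Step 1: search against definition.**

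| Type of event | SAP Appendix F search | Protocol 10.5.1 |
|---|---|---|
| New, unrelated cancer | Included | New malignant tumor |
| CLL/SLL/PLL (entry tumor) | Haematological query included, no exclusion | Not a new tumor |
| Richter's transformation | Haematological and lymphoma queries included, no exclusion | Not a new tumor |

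The two documents disagree on the last two rows. Appendix F does write exclusions where it wants them: the hemorrhage row drops laboratory terms, the other-leukopenia row drops the neutropenia terms, and the second malignancy row drops non-melanoma skin. An unstated exclusion of the study disease therefore cannot be assumed.

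**Step 2: can such an event reach the search?** It has to be recorded as an adverse event and fall in the TEAE window, from first dose to 30 days after last dose (SAP 13.1).

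- Clear progression is kept out by Protocol 10.3, and Section 9 makes transformation progressive disease. A clear-cut case should not be in the AE data.
- A doubtful case must be reported under the same section. This is the route in.
- Protocol 10.5.1 deals with transformation inside its malignancy-reporting guidance, so the protocol foresaw that the two could be confused.

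**Step 3: size per event.** Inputs are the planned cohort sizes in SAP 4.0: 26, 19, 12 and 12. SAP 13.1 counts a subject once, so one affected subject with no other hit in the category adds 1/n. The table assumes no true second cancer and x misclassified subjects. Intervals are exact (Clopper-Pearson) 95%.

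| Cohort | n | x = 0 | x = 1 | x = 2 |
|---|---|---|---|---|
| 1 | 26 | 0% (0 to 13.2) | 1/26 = 3.8% (0.1 to 19.6) | 2/26 = 7.7% (0.9 to 25.1) |
| 2 | 19 | 0% (0 to 17.6) | 1/19 = 5.3% (0.1 to 26.0) | 2/19 = 10.5% (1.3 to 33.1) |
| 3 or 4 | 12 | 0% (0 to 26.5) | 1/12 = 8.3% (0.2 to 38.5) | 2/12 = 16.7% (2.1 to 48.4) |

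The values of x are assumptions chosen to show the range. The documents give no count.

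**The case against.** The strongest reply is that the adverse event rules already do the filtering. Protocol 10.3 keeps clear progression out, Section 9 classes transformation as progression, and the baseline CLL is not an adverse event at all. This largely stands. A reader might infer from Appendix F that transformation and the CLL itself are being counted as second cancers, or that the rate is known to be biased upward. The documents support only the conditional: such an event would be counted if it were reported as a TEAE. The filter is incomplete because doubtful cases must be reported. The point is stronger for Richter's transformation, which 10.5.1 names, than for CLL progression.

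Second, 10.5.1 is a rule on reporting and seriousness, and Appendix F is an analysis search. That is correct. Still, 10.5.1 is where the protocol says which tumors are new, and the SAP offers no competing definition that would justify a different count.

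Third, the term lists of the queries are not in the documents, so it is an inference from the query names that they hold CLL or Richter's terms. The Appendix F text available here also points to a later section on major hemorrhage that is not present. Both are fair cautions, although the inclusion of the haematological query is explicit.

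Fourth, the analysis is descriptive, with no formal tests (SAP 7.1), and TEAEs are also tabulated by preferred term, so a reader could find a transformation term. An event may also properly appear in both efficacy and safety outputs, as a death can. These points lower the stakes. What remains is that the category label would be wrong.

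A reader might also infer that worsening of a cancer already in the medical history should be excluded. The documents do not support that. 10.5.1 uses such worsening as an example of a valid AE, and it explains new only as not the study tumor, its metastasis or its transformation. Removing these events could hide a safety signal.

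**Conclusion.** The mismatch is real but narrow. As written, the Appendix F search would classify a CLL/SLL/PLL or transformation event reported as a TEAE as a second primary malignancy, contrary to Protocol 10.5.1. Each affected subject would add 3.8 points in Cohort 1, 5.3 in Cohort 2 or 8.3 in Cohort 3 or 4.

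This rests on two assumptions: that the haematological and lymphoma queries contain the relevant terms, as their names suggest, and that at least one such event is reported as an adverse event within the TEAE window. If none is, the table is unaffected. A reader might expect a larger distortion in the relapsed/refractory cohorts, but the documents give no event counts by cohort to support that.

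**What to change.** Add one sentence to SAP Appendix F that applies to both second primary malignancy rows. It should exclude terms for the disease under study (CLL/SLL/PLL) and for its transformation (Richter's or prolymphocytic), on the basis of a documented medical review of the haematological and lymphoma hits before database lock. A haematological or lymphoma hit that the review judges to be a new tumor stays in the count. Worsening of a malignancy in the medical history also stays in. The review does not need to be blinded to outcome.

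The cost is a line of SAP text and a review of a few terms. No new data are needed and no sample size changes. The category rate can only stay the same or fall, and any excluded event remains visible by preferred term in the TEAE tables.
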